8. STUDY DRUG

8.1. Description of Investigational Agent

The ixazomib drug product is provided in strengths of 4.0, 3.0, and 2.3 mg capsules as the active boronic acid. The different dose strengths are differentiated by both capsule size and color as described below:

Dose Strength	Capsule Size	Capsule Color
4.0 mg	Size 4	lvory
3.0 mg	Size 3	Light gray
2.3 mg	Size 2	Light pink

For additional details, please see the ixazomib IB.

8.2. Study Drug Administration

8.2.1. Ixazomib Administration

All protocol-specific criteria for administration of study drug must be met and documented before drug administration. Study drug will be administered or dispensed only to eligible patients under the supervision of the investigator or identified sub-investigator(s). Patients should be monitored for toxicity, as necessary, and doses of ixazomib should be modified as needed to accommodate patient tolerance to treatment; this may include symptomatic treatment, dose interruptions, and adjustments of ixazomib dose (see Section on 8.2.3 for dose modifications).

Capsules of ixazomib will also be referred to as study drug. Study drug will be supplied by Millennium as capsules of 4.0, 3.0, and 2.3 mg ixazomib.

The prescribed administration of ixazomib doses in this study is 4.0mg ixazomib weekly in a 28 day cycle.

Patients should be instructed to swallow ixazomib capsules whole, with water, and not to break, chew, or open the capsules. Study drug should be taken on an empty stomach (no food or drink) at least 1 hour before or 2 hours after a meal. Each capsule should be swallowed separately with a sip of water. A total of approximately 8 ounces (240 mL) of water should be taken with the capsules.

Missed doses can be taken as soon as the patient remembers if the next scheduled dose is 72 hours or more away. A double dose should not be taken to make up for a missed dose. If the patient vomits after taking a dose, the patient should not repeat the dose but should resume dosing at the time of the next scheduled dose.

8.2.2. Ixazomib Destruction

Investigational ixazomib (expired or end of study) should be destroyed on site according to the UAMS Research Pharmacy standard operating procedure. Be sure to document removal and destruction on drug accountability logs.

8.2.3. Dose-Modification Guidelines

8.2.3.1. Criteria for Beginning/Delaying Treatment Cycles & Dose Modifications for Treatment Assoc.Toxicity

Treatment with ixazomib will use a cycle length of 28 days. For a new cycle of treatment to begin, the patient must meet the following criteria:

- ANC must be \geq 1,000/mm³.
- Platelet count must be \geq 75,000/mm³.
- All other non-hematologic toxicities should, at the physician's discretion, generally be recovered to patient's baseline condition or Grade 1 or lower

If the patient fails to meet the above-cited criteria for initiation of the next cycle of treatment, dosing should be delayed for 1 week. At the end of that time, the patient should be reevaluated to determine whether the criteria have been met. If the patient continues to fail to meet the above-cited criteria, delay therapy and continue to re- evaluate. The maximum delay before treatment is discontinued is 3 weeks.

8.2.3.2. Ixazomib Dose Adjustment Schedule

Dose Level	Dose
Starting Dose	4.0 mg
-1	3.0 mg
-2	2.3 mg
-3	Discontinue

8.2.3.3. Ixazomib Dose Adjustments for Hematological Toxicities

Ixazomib Dose Adjustments for Hematologic Toxicities				
Criteria	Action			
 Within-Cycle Dose Modifications If platelet count ≤ 30 × 10⁹/L or ANC ≤ 0.50 × 10⁹/L on a ixazomib dosing day (other than Day 1) 	 Ixazomib dose should be withheld. Complete blood count (CBC) with differential should be repeated at least every other day until the ANC and/or platelet counts have exceeded the prespecified values (section 8.3.1 above on at least 2 occasions. Upon recovery, ixazomib may be reinitiated with 1 dose level reduction. 			
 Dose Modifications for Subsequent Treatment Cycles Delay of > 2 weeks in the start of a subsequent cycle due to lack of toxicity recovery as defined in Section 8.3.1 ANC < 1.0 × 10⁹/L, platelet count < 75 × 10⁹/L, or other nonhematologic toxicities > Grade 1 or not to the patient's baseline condition Dose Modifications for Subsequent Treatment Cycles 	 Hold ixazomib until resolution as per criteria Section 8.3.1 Upon recovery, reduce ixazomib 1 dose level. The maximum delay before treatment should be discontinued will be 3 weeks or at the discretion of the PI. 			
All hematologic toxicities	 For hematologic toxicity that occurs during a cycle but recover in time for the start of the next cycle,: If dose was reduced within the cycle, start the next cycle at that same dose. If due to toxicity timing, ie, after Day 22 dosing thus a dose reduction was not required at that point in the cycle, reduce ixazomib by 1 dose level at the start of the next cycle. Do not reduce the dose both within a cycle and at the start of the next cycle for the same most severe toxicity. 			

Ixazomib Dose Adjustments for Non-Hematological Toxicities 8.2.3.4.

Adverse Event (Severity)	Action on Study Drug	Further Considerations
Peripheral Neuropathy: Grade 1 peripheral neuropathy	No action	Grade 1 signs and symptoms: asymptomatic; without pain or loss of function; clinical or diagnostic observations only [14]
New or worsening Grade 1 peripheral neuropathy with pain or Grade 2	 Hold study drug until resolution to Grade ≤ 1 or baseline 	Grade 2 signs and symptoms: Moderate symptoms; limiting instrumental activities of daily living (ADL) [14]
New or worsening Grade 2 peripheral neuropathy with pain or Grade 3	 Hold study drug until resolution to Grade ≤ 1 or baseline Reduce study drug to next lower dose upon recovery 	Grade 3 signs and symptoms: severe symptoms; limiting self-care ADL; assistive device indicated [14]
New or worsening Grade 4 peripheral neuropathy	Discontinue study drug	
Grade 2 Rash	Symptomatic recommendations as per section 8.2.5	The investigator and project clinician may discuss considerations for dose modifications and symptom management.
Grade 3 nonhematologic toxicity judged to be related to study drug	 Hold study drug until resolution to Grade < 1 or baseline Reduce study drug 1 to next 	Symptomatic recommendations noted in Section 8.2.5
< Grade 1 or baseline within 4 weeks	lower dose upon return to < Grade 1 or baseline	
Subsequent recurrence Grade 3 that does not recover to < Grade 1 or baseline within 4 weeks	 Hold study drug until resolution to Grade < 1 or baseline Reduce study drug to next lower dose 	Monitor closely, take appropriate medical precautions, and provide appropriate symptomatic care
Grade 4 nonhematologic toxicities judged to be related to study drug	Consider permanently discontinuing study drug	Exceptions are cases in which the investigator determines the patient is obtaining a clinical benefit

Once ixazomib is reduced for any toxicity, the dose may not be re-escalated.

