4. STUDY DESIGN

4.1. Overview of Study Design

This is a phase 2 study designed to examine the bone anabolic effect of the next generation proteasome inhibitor, ixazomib, in relapsed/refractory myeloma patients. Treatment consists of ixazomib 4 mg on days 1, 8, 15, 22 of a 28-day cycle, for a maximum of 6 cycles).

General eligibility criteria may be assessed prior to the formal Screening period if it is part of standard clinical practice. However, per the Schedule of Events, formal screening will occur during the Screening period, which may last for up to 35 days prior to initiating study treatment. Determination of relapsed/refractory disease as an entry criterion may be based on patient data obtained during or following the patient's most recent prior antineoplastic therapy.

Study drug (ixazomib 4.0 mg) will be given on Days 1, 8, 15, 22 of a 28- day cycle for a maximum of 6 cycles. Dose modifications may be made based on toxicities during treatment. Patients will be discontinued from the study for progressive disease or unacceptable toxicity.

Treatment periods will be defined as 28-day cycles. Patients will be seen once per treatment cycle (Day 1) during their participation in the active treatment of the study. More frequent follow-up would be only as clinically indicated at the discretion of the treating physician.

Patients will be assessed for disease response and progression. Response will be assessed according to the International Myeloma Working Group (IMWG) criteria (see APPENDIX A) for all patients every 4 weeks for a maximum of 6 cycles (unless disease progression or unacceptable toxicity).

ECOG performance score (APPENDIX B), adverse events (AEs), laboratory values, and vital sign measurements will be collected and assessed throughout the study. Toxicity will be evaluated according to National Cancer Institute Common Terminology Criteria for Adverse Events (NCI CTCAE), version 4.03, effective date 14 June 2010.

Patients will attend an End of Treatment (EOT) visit after completion of their 6 cycles (or at study discontinuation due to progressive disease, unacceptable toxicity, or other reason) and will continue to be followed for survival.

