6. TREATMENT PLAN

All baseline assessments, labs, and bone marrow biopsies are to be completed within 35 days of enrollment. Radiological studies are to be completed within 60 days prior to enrollment.

Study drug (ixazomib 4.0 mg) will be given on Days 1, 8, 15, 22 of a 28- day cycle for a maximum of 6 cycles.

For a new cycle of treatment to begin, the patient must meet the following criteria:

- ANC must be $\geq 1,000/\text{mm}^3$.
- Platelet count must be \geq 75,000/mm³.
- All other non-hematologic toxicities should, at the investigator's discretion, generally be recovered to patient's baseline condition or Grade 1 or lower.

Dose modifications may be made based on toxicities during treatment described in detail in section 8.2.3. Treatment periods will be defined as 28-day cycles. Patients will be seen in clinic once per treatment cycle (Day 1) during their participation in the active treatment of the study. More frequent follow-up would be only as clinically indicated at the discretion of the treating physician.

Patients will be assessed for disease response and progression. Response will be assessed according to the IMWG criteria (see APPENDIX A) for all patients every 4 weeks for a maximum of 6 cycles (unless disease progression or unacceptable toxicity).

Patients will attend an End of Treatment (EOT) visit after completion of their 6 cycles (or at study discontinuation due to progressive disease, unacceptable toxicity, or other reason) and will continue to be followed for survival. Follow-up for survival after end of treatment will be limited to contact via telephone approximately annually to verify the patient's disposition. Verification of the patient's disposition may be performed by medical record review if the patient was seen in clinic at UAMS within 3 months of the scheduled follow-up interval.

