6.2. Laboratory tests

Laboratory tests (CBC with differential, BMP, LFTs, Uric Acid, Albumin, CRP, Pregnancy Test (WOCBP)), bone marker tests (BALP, Osteocalcin, NTX, Vitamin D 25), and myeloma lab tests (Serum Protein Electrophoresis, Serum Quantitative Immunoglobulins, Serum Free Light Chains, Serum IFE and/or Urine Beta-2-Microglobulin) will be performed at baseline, on day 1 of cycles 2-6, and at end of study. BNP and TSH will be performed at baseline and end of study only.

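### The within-cycle blood-count hold rule applies on Days 8, 15 and 22, but no blood count is scheduled on any of those days

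*Combined protocol and SAP*

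**What the plan says.** Section 4.1 gives ixazomib on Days 1, 8, 15 and 22 of a 28-day cycle, for at most 6 cycles. In Section 8.2.3.3 the within-cycle rule withholds the dose if platelets are ≤ 30 × 10⁹/L or ANC is ≤ 0.50 × 10⁹/L "on a ixazomib dosing day (other than Day 1"). After a hold, the blood count "should be repeated at least every other day until the ANC and/or platelet counts have exceeded the prespecified values".

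The visit and laboratory schedule reads differently:

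- Section 6: "Patients will be seen in clinic once per treatment cycle (Day 1) during their participation in the active treatment of the study".
- Section 4.1, and Section 6 in the same terms: "More frequent follow-up would be only as clinically indicated at the discretion of the treating physician".
- Section 6.2, for the laboratory panel that includes the CBC with differential: "will be performed at baseline, on day 1 of cycles 2-6, and at end of study".
- Section 7: the table marks the CBC at baseline, in a single column for Cycles 1-6 that names no day, and at end of treatment.

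Section 8.2.1 adds: "All protocol-specific criteria for administration of study drug must be met and documented before drug administration". Under thrombocytopenia and neutropenia, Section 8.2.5 refers back to the protocol for regular count monitoring and leaves any further testing to standard practice.

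**The concern.** The hold rule needs a platelet or neutrophil count on the dosing day, and the schedule supplies none on the days when the rule applies. Section 8.2.6 lets a full cycle of capsules go home with the patient. A patient handled exactly to the schedule could therefore take the Day 8, 15 and 22 doses without a visit or a count, and be below the protocol's own hold thresholds without anyone knowing.

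Section 8.2.5 says that both cytopenias may be severe. It also says that neutropenic nadirs commonly resolve by the next scheduled cycle or after a short delay. A nadir that forces a delay would be seen on Day 1, but one that has already resolved may not be.

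There is also a consequence for the data. Toxicity found on an unscheduled count would be recorded (Sections 10.1 and 10.2), and a reduced dose may not be raised again (end of Section 8.2.3.4). Both recorded haematological toxicity and later dose can therefore depend on how often the treating physician chooses to test.

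**Working it through.** The plan states no figure to reproduce. The check is a count of days, followed by a search for any other required count that could fill the gap.

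**Rule days.** Dosing days are 1, 8, 15 and 22 (Section 4.1), and the rule excludes Day 1 (Section 8.2.3.3).

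- Planned doses per patient: 4 × 6 = 24.
- Rule days per patient completing 6 cycles: (4 − 1) × 6 = 18.
- Ceiling for the trial, if all 20 patients complete 6 cycles: 18 × 20 = 360.

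**Scheduled counts on rule days.**

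| Reading of the schedule | Scheduled counts during treatment | Rule days covered |
|---|---|---|
| Section 6.2 | Day 1 of cycles 2-6 | 0 of 18 |
| Section 7 table, read with the Day 1 visit in Sections 4.1 and 6 | Day 1 of cycles 1-6 | 0 of 18 |

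Across the trial the coverage is 0 of at most 360. The two readings differ only on a count at Day 1 of cycle 1, which is not a rule day.

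**Age of the latest scheduled count, cycles 2-6.** Day 8: 8 − 1 = 7 days. Day 15: 15 − 1 = 14 days. Day 22: 22 − 1 = 21 days. This concerns 3 × 5 = 15 doses per patient. No age is given for cycle 1, because Sections 6.2 and 7 disagree on whether a count is taken then.

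**Other counts the protocol requires.**

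1. The every-other-day counts in Section 8.2.3.3 may fall on a later dosing day, but they are repeats that follow a hold. They track recovery and cannot provide the first detection.
2. After a failed cycle start, Section 8.2.3.1 delays dosing for a week and then: "At the end of that time, the patient should be reevaluated to determine whether the criteria have been met". That takes place before the delayed cycle's Day 1 dose, so it is not on a rule day.
3. The end-of-treatment count comes after completion or discontinuation.

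**What the rule itself presupposes.** Section 8.2.3.3 also has a row that begins: "For hematologic toxicity that occurs during a cycle but recover in time for the start of the next cycle". One branch of that row deals with a dose already reduced within the cycle. Under the haematological rules, such a reduction follows a low count found within the cycle, so the table assumes counts that the schedule does not contain.

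**Section 8.2.1, read both ways.** If the hold thresholds are among the criteria to be documented before administration, the schedule omits the counts needed to document them. If they are not, first detection rests on discretionary or standard-practice testing. The rule and the schedule fail to match on either reading.

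**Size in patients.** The documents give no rate for platelets ≤ 30 or ANC ≤ 0.50 × 10⁹/L. The nearest figures are any-grade events in the pooled oral single-agent studies (Section 1.1.4.5): thrombocytopenia 68/201 = 33.8% and neutropenia 29/201 = 14.4%. They mix doses and schedules and are not threshold rates, so no number of affected patients is derived from them.

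**The case against.** The strongest reply is that the rule is conditional. It says what to do with a low count and does not order a count on every dosing day. The protocol also says where interim counts come from: toxicity monitoring as needed (Section 8.2.1), extra follow-up when clinically indicated (Sections 4.1 and 6), and additional testing under standard practice (Section 8.2.5). On this view the rule can be carried out, and a patient managed to the whole protocol would be tested. If Section 8.2.1 covers the hold thresholds, dosing without a count would be a deviation and the fault would lie only in an incomplete table. The primary endpoint, change in serum osteocalcin, is not directly involved.

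Some of this stands:

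- The rule can be applied wherever a physician chooses to test, and the Section 7 column names no day. That counts fall only on Day 1 is inferred by reading Section 7 with Sections 4.1, 6 and 6.2.
- Toxicity first seen at a failed cycle start and resolved during the delay could fit part of the recovery row. Only the branch on reduction within a cycle clearly needs an interim count.
- Section 8.2.5 refers to the Investigator's Brochure for further detail on managing adverse events, and that document is not available here.

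It does not remove the mismatch. Section 8.2.5 leads back to the same Day 1 schedule and fixes no timing for anything beyond it. Follow-up prompted by clinical indication is a weak trigger for a rule that turns on a laboratory value. An incomplete table would itself be the defect described here.

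**Conclusion.** The concern holds and should be fixed before the plan is relied on. The hold rule operates on 18 days per patient completing 6 cycles, and the schedule provides a count on none of them. Followed as written, the plan can let doses be taken below its own hold thresholds without detection.

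The figure of 18 is a maximum per patient. Early discontinuation lowers it, but the number covered stays at 0. The conclusion assumes that the undated Section 7 column refers to the once-per-cycle Day 1 visit, and no section of the protocol says otherwise. It does not claim that low counts would always be missed, and it puts no number on the patients affected. The sample-size calculation is unaffected.

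**What to change.** Reconcile Sections 4.1, 6, 6.2, 7, 8.2.1, 8.2.3.3, 8.2.5 and 8.2.6 so that the hold rule and the blood-count schedule agree. Either align the days, or state explicitly on which counts the rule operates. State also whether the hold thresholds are among the criteria that Section 8.2.1 requires to be documented before a dose. Which side changes is for the sponsor's clinicians to decide; this review proposes no clinical rule.

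Two minor corrections belong in the same edit:

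- Resolve the difference between Sections 6.2 and 7 on a cycle 1 count.
- Correct the references in Section 8.2.3.3 to a Section 8.3.1 that does not exist, once the sponsor confirms that Section 8.2.3.1 is meant.

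The cost is one protocol amendment and, if the schedule is the side that changes, some additional routine blood counts.

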8.2.3.6. Permitted Concomitant Medications and Procedures

The following medications and procedures are permitted during the study:

- Antiemetics, including 5-HT3 serotonin receptor antagonists, may be used at the discretion of the investigator.
- Loperamide or other antidiarrheal should be used for symptomatic diarrhea at discretion of the investigator. The dose and regimen will be according to institutional guidelines. IVF should be given to prevent volume depletion.
- Growth factors (eg, granulocyte colony stimulating factor [G-CSF], granulocyte macrophage-colony stimulating factor [GM-CSF], recombinant erythropoietin) are permitted. Their use should follow published guidelines and/or institutional practice; however, alternative usage may be reviewed with the Millennium Clinical or Medical

Representative . Erythropoietin will be allowed in this study. Their use should follow published guidelines and/or institutional practice.

- Patients should be transfused with red cells and platelets as clinically indicated (except as noted in 8.2.4) and according to institutional guidelines.
- Antiviral therapy such as acyclovir may be administered if medically appropriate.
- Patients who experience worsening neuropathy from baseline may be observed for recovery, and have dose reductions/delays as indicated in the protocol, and any supportive therapy or intervention may be initiated as appropriate at the discretion of the investigator.
- Supportive measures consistent with optimal patient care may be given throughout the study.

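### Section 8.2.3.4: the hold for Grade 1 peripheral neuropathy with pain has a release that does not mention pain, so by grade number it is met as soon as the hold starts

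*Combined protocol and SAP*

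**What the plan says.** The first peripheral neuropathy row in the table of Section 8.2.3.4 (non-haematological toxicities) covers Grade 1 and calls for no action. Its comment column describes Grade 1 as "asymptomatic; without pain or loss of function; clinical or diagnostic observations only".

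The second row is triggered by "New or worsening Grade 1 peripheral neuropathy with pain or Grade 2" and its action is "Hold study drug until resolution to Grade ≤ 1 or baseline". It gives no dose reduction.

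The third row is triggered by "New or worsening Grade 2 peripheral neuropathy with pain or Grade 3". It uses the same release wording but also steps the drug down one dose level on recovery.

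Four other places bear on restarting. Section 6 says that non-haematological toxicities should, "at the investigator's discretion, generally be recovered to patient's baseline condition or Grade 1 or lower", before a new cycle, and Section 8.2.3.1 repeats the criterion ("generally be recovered to patient's baseline condition or Grade 1 or lower"). Section 8.2.1 says that "doses of ixazomib should be modified as needed to accommodate patient tolerance to treatment". Section 8.2.3.6 says: "Patients who experience worsening neuropathy from baseline may be observed for recovery, and have dose reductions/delays as indicated in the protocol".

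**The concern.** A hold rule sets the least that must happen before the drug is given again. In the second row, one way in is Grade 1 neuropathy that has become painful. The way out is stated by grade or by return to baseline, with no word on pain. If the way out is already open at entry, the rule can be followed to the letter and have no effect.

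What is at stake is a patient being re-dosed at an unchanged level while the neuropathic pain that prompted the hold is still present. This concerns dosing safety. It does not bear on how the osteocalcin endpoint is tested or on how the 20 patients were justified.

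**Working it through.** No figure in the plan depends on this rule, so the check is logical: is the release true at the moment each trigger is met?

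1. **Form of the release.** It is met if the grade is 1 or lower, or if the patient is back to baseline. Because the two parts are joined by an or, either is enough.

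2. **Grade 1 with pain, read by grade number.** The grade at onset is 1, and 1 ≤ 1, so the first part is true at once. Return to baseline is not needed. The required hold has zero duration, and with no reduction in the row the same dose may resume.

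3. **Grade 1 with pain, read by the description in the row above.** If Grade 1 in the release means the painless state of the first row, the patient must lose the pain before restarting, and the hold does what it should. This reading has to be brought in from a comment in another row.

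4. **Grade 2 limb of the same row.** The grade at onset is 2, and 2 > 1, so the first part is false and the patient must improve or return to baseline. The limb works.

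5. **Third row.** The trigger is Grade 2 with pain or Grade 3, so the grade part is false at onset. A fall in grade or return to baseline is required, and a dose reduction follows. The row works.

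6. **Other restart text.** The new-cycle criterion in Sections 6 and 8.2.3.1 is set by baseline or grade and is silent on pain. It also governs only the start of a cycle, while dosing is weekly on Days 1, 8, 15 and 22. Section 8.2.1 is a general tolerance rule with no release condition. Section 8.2.3.6 refers dose delays back to the protocol's own rules. None supplies a pain-free restart.

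**Scale.** Table 3 in Section 1.1.4.5 reports peripheral neuropathy in 21 of 201 single-agent oral patients: 21/201 = 0.1045, which the table rounds to 10%. The exact 95% interval is 6.6% to 15.5%. For the 20 patients in Section 4.2, 20 × 0.1045 = 2.1 (1.3 to 3.1) with neuropathy of any grade. The table gives no split by grade or by pain, so the number entering the painful Grade 1 limb cannot be derived. The pool also covers one preferred term, various phase 1 doses and schedules, and several malignancies, so it gives an order of magnitude only.

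**The case against.** The strongest reply is that the table treats Grade 1 and Grade 1 with pain as two separate states with different actions. Release to Grade 1 or lower then means going back to the first row, which is painless. The word resolution supports this, since it implies leaving the state that triggered the hold. Pain is used as a separate modifier elsewhere too: Section 5.2 excludes Grade 2 with pain, and the third row does the same at Grade 2. This stands as the likely intent, and most investigators would probably reach it. It remains an inference, because the release cell does not state it.

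The second reply is clinical judgement. Sections 8.2.1, 8.2.3.1 and 8.2.3.6 let the physician keep holding, and the trial is run within one institution, so inconsistency between sites is a weak worry. That also stands. It limits the consequence but does not set a minimum.

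Three stronger readings are tempting, and the documents support none of them:

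- A reader might infer that the trigger and the description of Grade 1 flatly contradict each other, so that no consistent reading exists. The separate-states reading is consistent; the fault is that it is unstated.
- A reader might infer that the third row is defective because its release wording is the same. It is not: its trigger lies above the release grade, and a dose reduction is required.
- A reader might infer that the protocol compels re-dosing in pain. It permits this on a literal reading; nothing requires it.

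**Conclusion.** The point holds for one limb of one row: new or worsening Grade 1 neuropathy with pain. Read by grade number, the release there is already satisfied at onset, and the reading that makes the hold meaningful is likely but not written down. This is a minor dosing-safety correction.

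The conclusion rests on the table wording alone. Both cells appear intact in the text, and the same release wording recurs in the next row, so it does not look like an extraction fault. How many patients would be affected is unknown. Any figure would need an assumed share of neuropathy that is Grade 1 and painful, and the documents offer no basis for one. The Grade 2 limb and the third row work as written. The sample size and the planned analysis method are unaffected.

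**What to change.** In the second neuropathy row of the table in Section 8.2.3.4, change the release to: *Hold study drug until resolution to Grade ≤ 1 without pain, or baseline*. Leave the third row as it is.

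The cost is one cell reworded by amendment, with no new visits or tests. The downside is small: some holds may last longer. Because both limbs share the cell, that includes a patient who falls from Grade 2 to a painful Grade 1. Section 8.2.3.1 ends treatment after a three-week delay in starting a cycle, so a longer hold could occasionally bring a patient's exit forward.
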